## GLOSSARY OF ABBREVIATIONS

BASEC	Business Administration System for Ethical Committees
CSA	Cross Sectional Area
CRF	Case Report Form
EMG	Electromyography
FOPH	Federal Office of Public Health
H:Q Ratio	Ratio between Hamstrings and Quadriceps strength
HMF	Host Mesh Fitting
HRA	Human Research Act
HRO	Ordinance on Human
IMU	Inertial Measurement Unit
iPhone	Mobile Phone by Apple Inc.
iOS	Mobile Operating System by Apple Inc.
ISAK	International Society for the Advancement of Kinanthropometry
PI	Principal Investigator
1RM	One Repetition Maximum
SCMI	Swiss Centre for Musculoskeletal Imaging
(S)AE	(Serious) Adverse Event
ZHAW	Zürcher Hochschule für angewandte Wissenschaft
SNCTP	Swiss National Clinical Trials Portal
watchOS	Operating System for the Apple Watch
BASEC	Business Administration System for Ethical Committees

# 1 BACKGROUND AND PROJECT RATIONALE

Musculoskeletal diseases and pain are a major concern and financial burden for the Western society due to the progressively aging population, and an increasing percentage of people working in a seated position [4, 5]. Additionally, the incidences of acute injuries to the musculoskeletal system remain the most frequently reported occupational injuries in the healthy population, with often long-term consequences for patients and associated medical costs [6].

## 1.1. Fitness and strength training

Muscular strength training interventions have long been a cornerstone in the prevention, non-surgical management and rehabilitation of the entire spectrum of musculoskeletal injuries and diseases in athletes, healthy adults, patients and the elderly [7-9]. Strength training has been shown to enhance general fitness and the deposition of bone mass in healthy adults [9], improve activity levels and independence of senior adults [10], enhance the performance of competitive athletes [11], as well as help in the prevention and rehabilitation of musculoskeletal injury and disease [8]. Furthermore, a recent large-scale epidemiological study in over 80,000 adults suggested a 31% reduction of cancer mortality in subjects that adhered to strength training over and above the generic physical activity targets [7].

The key goal of muscular strength training is to regain, maintain or enhance musculoskeletal function. Yet, despite the widespread use of muscular strength training across sports and health care practice, there remains a fundamental lack of understanding with regards to the relationship between subject-specific anatomy, musculoskeletal function and different strength exercises to ensure training safety and efficiency because of limitations in assessing these parameters outside the research setting. Consequently, fitness instructors, coaches, physiotherapists and clinicians continue making training recommendations based on subjective and generalised guidelines, with possibly ineffective or sometimes harmful consequences for individual patients and athletes.

## 1.2. Computational musculoskeletal models

Computational models of the musculoskeletal system have played a key role in sports and clinical biomechanics to help understand how different types of strength exercises and execution forms are affecting musculoskeletal function [12]. Computational models of the musculoskeletal system in combination with data from marker-based optical motion capture, ground reaction forces and/or Electromyography (EMG) have been applied to strength training to analyse the best choice and execution form to avoid injury [13-18]; the internal loading state of differently sized people using the same exercise machines [19]; as well as changes in musculoskeletal loading for different exercises and execution forms [18].

Yet, one key challenge that remains to be addressed is the capturing of subject-specific anatomical differences. Numerical techniques to fit so-called generic models to subject-specific anatomical data have remained computationally very involved and too time-consuming for widespread application outside the research setting. It remains commonly assumed in sports science that a limited number of body surface trajectories (e.g. bony anatomical landmarks) sufficiently reflect the subject-specific anatomy of the entire musculoskeletal system; which is problematic especially when investigating muscular imbalances, postural alignment and musculoskeletal limitations or gains due to strength training interventions.

In preliminary research, post-doctoral scientist [name] has assessed the feasibility of fitting generic musculoskeletal models to a limited number of subject-specific body surface data using a free-form deformation technique called Host Mesh Fitting (HMF) [20-22]. The HMF technique is a geometric free-form deformation technique for fitting generic anatomically-based musculoskeletal models to a limited number of 3D body surface data. The HMF objective function is set up to find the optimum mesh nodal parameters that minimise the Euclidean distances between the subject-specific data points and their projections onto the surface mesh of the generic musculoskeletal model in a least-square sense. The position and deformation of the embedded soft-tissue muscle-tendon structures are derived from the deformation of the skin

mesh. The HMF technique was initially introduced to develop high-order finite element models of individual organs, and later applied and validated for predicting the deformation of muscle-tendon structures in the lower limbs during walking [20].

In the scope of a validation study using data from Magnetic Resonance Imaging (MRI) as gold standard, a generic anatomically-based model was fitted to subject-specific data of six children with cerebral palsy and five children without cerebral palsy. The HMF led to better predictions of muscle volumes and lengths than conventional scaling, with the average error between MRI and HMF being less than 10% for muscle lengths and less than 30% for muscle volume [22]. Further improvements are expected by considering individual body composition (i.e. somatotype) and developing a library of musculoskeletal models for different body shapes and population groups.

### **1.3. Mobile monitoring technology**

Mobile monitoring technology, including Inertial Measurement Units (IMU) and optical image capture technology, are becoming readily accessible in ubiquitous devices such as smartphones and smartwatches [23-27] and have become a global research topic to monitor strength training progress. However, while some investigations on commercially-available mobile technology exist to detect exercise type and repetition count, there is still a lack of scientifically-based research to reveal insights into exercise safety and efficiency based on biomechanical principles [28]. Furthermore, the assessment of execution diversity between strength exercises and individual subjects continues to be a key challenge [27]. In comparison to endurance activities, such as outdoor running, the intensity estimation and execution diversity of strength training workouts requires more advanced numerical analysis of the available data [25].

The PI and his research group have started analysing the validity and reliability of commercially available devices in combination with an in-house developed, numerical algorithm for the mobile operating system by Apple Inc. (iOS) to assess musculoskeletal function during strength training outside the research or clinical setting. In particular, an advanced iOS motion-recognition application, named *iOS Strength Control app*, was developed using data from the Apple Watch to identify the type of exercise, repetition count and One Repetition Maximum (1RM) [29-34]. Thereby, research has clearly shown that the quantification of 1RM, as the maximum load that can be lifted through a full range of motion, is fundamentally important when it comes to the design of safe and efficient resistance training programs [31, 35, 36].

The validity, reliability and accuracy of the *iOS Strength Control app* was assessed outside the laboratory setting in 30 physically healthy subjects, all participating in their own weight training program 1-4 days per week, and for three barbell exercises (i.e. deadlift, bench press, back squat) [33]. Excellent accuracy was demonstrated in exercise recognition and repetition count; yet further development and validation are required to improve the accuracy and reliability in the assessment of exercise execution (joint motion and velocity) and 1RM. Here, previous research has shown that the accuracy in the calculation of 1RM depends on the velocity and joint range of motion during exercise execution, which require more advanced numerical algorithms in biomechanics to be derived.

### **1.4. Project rationale**

The rationale of this 4-year project which started at the Swiss Federal Institute of Sport Magglingen (SFISM) and continues at the Zürcher Hochschule für angewandte Wissenschaften (ZHAW) is to apply and validate novel approaches in subject-specific anatomically-based modelling and mobile monitoring to an intervention study in healthy volunteers to predict adaptation in muscle strength and muscle size due to different strength training volume. Individual strength training guidelines, and monitoring of adherence to exercise guidelines for ensuring training safety and efficiency, remain difficult because of limitations in assessing subject-specific anatomical and functional parameters in the training-specific setting. As a consequence, strength training continues to be largely based on subjective expertise, with possibly ineffective or even harmful consequences for individual athletes and patients.

In the scope of this study, we will conduct an 8-week strength training intervention study of key muscle-tendon groups associated with knee joint stability in three study groups with different levels of training volume, with the goal to predict changes in muscle strength and muscle size in relation to training-specific parameters based on subject-specific musculoskeletal modelling and mobile monitoring. Based on subject-specific data MRI in a sub-group of participants, we will further be able to refine validate the HMF technique with the highest accuracy possible.

The outcome will provide new insights into the relationship between subject-specific anatomy, musculoskeletal function and strength training design, which will advance current knowledge in sports science and help to inform strength training recommendations for individual athletes and patients. Technically, we will be able to answer the key research question ‘How accurately can changes in muscle strength and muscle size be predicted based on training volume using the novel computational and mobile monitoring technologies?’. The insights and technological advances gained from this study will provide novel means for coaches, clinicians and physiotherapists to answer key questions, such as ‘Which strength and rehabilitation training design is best suited for an individual subject to maximise training benefits?’. Thereby, the application of research outcomes will not only benefit athletes but there is tremendous potential also in advancing community-based initiatives and public health services by informing and supporting safe and effective strength training practice.

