## 2 PROJECT OBJECTIVES AND DESIGN

### 2.1 Hypothesis and primary objective

Hypothesis: It is hypothesized that advanced subject-specific musculoskeletal modelling in combination with mobile monitoring technology as embedded in the iPhone and Apple Watch allow for accurate prediction of changes in muscle strength and muscle size in the lower limbs following an 8-week strength training intervention of key muscle-tendon groups associated with knee joint stability.

Primary Objective: Prediction of changes in muscle strength in the lower limbs due to different strength training volumes by means of the advanced computational modelling, biomechanical analysis and mobile monitoring technology. Of particular interest is the prediction of 1RM and the prediction of the ratio between hamstrings and quadriceps strength (H:Q ratio) compared against isokinetic strength tests as gold standard. Research has clearly shown that the quantification of 1RM is fundamentally important when it comes to the design of safe and efficient resistance training programs. Improved accuracy in the 1RM prediction compared to preliminary studies (i.e. mean %error of 0.27% in 60% and 7.81% in 80% 1RM assessment [29-34]) is expected through the consideration of data from optical motion capture as well as the additional consideration of subject-specific musculoskeletal anatomy from computational modelling.

Secondary Objective: Assessment of changes in muscle size in the lower limbs due to different strength training volumes using the HMF technique. Of particular interest is the prediction of muscle volume using the HMF technique compared against data from MRI as gold standard, as well as the prediction of adaptation in hamstrings and quadriceps CSA due to the strength training intervention using HMF versus data from ultrasound, respectively. Improved accuracies in the assessment of muscle size compared to preliminary studies (i.e. more than 70% accuracy in muscle volume [22]) are expected through the additional data from anthropometric measurements and the matching of generic model to the study-specific population group including gender.

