Study parameters: Anthropometric parameters include body height, body weight, segmental circumferences, somatotype, body shape, muscle CSA and muscle volume of the lower limbs. Anthropometric parameters will be assessed by means of HMF fitting in combination with data from 3D body scanning and anthropometric measurements according to ISAK standards. Changes in CSA of the hamstrings and quadriceps will be compared between HMF and data from ultrasound before and after strength training intervention. Strength- and training-specific parameters include joint motion, joint acceleration, total joint moments, repetition count, 1RM and H:Q ratio. Strength- and training-specific parameters will be assessed by means of biomechanical analysis using data from optical motion capture and the *iOS Strength Control app*, and compared against data from isokinetic strength tests as gold standard. Additionally, data from MRI of the lower limbs will be acquired in a sub-group of 12 participants (6F, 6M), who will be scheduled for one visit to the imaging facilities of the Swiss Centre for Musculoskeletal Imaging (SCMI) at the Balgrist Campus Zurich. The SCMI provides a highly specialized open access musculoskeletal imaging infrastructure, with a 7T Magnetom Terra and 3T Magnetom Prisma MRI device (Siemens) that can be booked per hour, including imaging support through a professional radiographer. Scan parameters are defined in line with previous research by our group [21]. Participants will be reimbursed for travelling costs.

This is a single-centre study that will be conducted at the research facilities of the ZHAW.

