Derivation of muscle volume and CSA based on MRI and computational modelling will be done using the open-source modelling environment OpenCMISS ([www.opencmis.org](http://www.opencmis.org)). OpenCMISS is an interactive computational modelling environment for Continuum Mechanics, Image analysis, Signal processing, and System identification, which has extensively been used for high-order subject-specific modelling of the musculoskeletal system. It provides generic model libraries, numerical algorithms and image processing tools for anatomically-based modelling and biomechanical analysis of muscle-tendon deformation [20-22]. Thereby, the present study will extend on previous efforts to derive muscle volume using the HMF technique by adjusting the HMF objective function to incorporate subject-specific thickness of the skin layer based on anthropometric measurements, as well as better matching of the generic musculoskeletal model to the target population group (i.e. age group and gender). For validation purposes, muscle

boundary surfaces will be manually segmented from the MRI data and muscle volumes will be derived by performing numerical quadrature over the parameterised muscle boundary surfaces. The resulting muscle volumes of hamstrings, quadriceps and triceps surae will be compared between MRI and the fitted results from HMF; while data from ultrasound will provide means to validate the accuracy of the predicted adaptation in CSA of hamstrings and quadriceps due to the strength training intervention.

Digital data is safely stored on the secured server architecture at the ZHAW with restricted access to study staff only (see also Section 7). Collected material, including signed consent forms and participant identification list, are safely stored at the ZHAW in locked cabinets. Expected biases to the project include gender, subject-specific training expertise and skin marker artefacts during optical motion capture. The sample size and population group are specified to allow the analysis of gender-specific differences on study results. Thereby, the inclusion/exclusion criteria and study protocol, including a training-related questionnaire, are defined to minimize the bias of training experience; and the functional calibration procedure, that will be employed in this study for optical motion capture, has been shown to minimise the effect of skin marker artefacts on kinematic analysis results [15, 48].

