HMF 16.5 (2.58) cm^3/kg, p-value > 0.05), respectively [22]. It is expected that the accuracy in the predicted muscle volume is improved in the present study by fitting a generic musculoskeletal model to subjects of similar age and gender, and without significant musculoskeletal impairments, as well as additionally considering subject-specific somatotype based on anthropometric measurements. ANOVA will be performed to analyse the pairwise differences in muscle volumes between the HMF and MRI-based results; and to analyse the pairwise differences in the predicted adaptation of hamstrings and quadriceps CSA between HMF and data from ultrasound before and after strength training intervention, respectively. The data from female and male participants will be analysed combined, as well as independently as two different groups.

The level of significance will be set at  $p < 0.05$  for all statistical tests.

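### The plan does not settle whether the 12 MRI sets that validate HMF may also refine it, and has no version freeze or out-of-sample error, so the reported HMF-MRI accuracy may be optimistic

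*Combined protocol and SAP*

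**What the plan says.** **Use of the MRI.** Section 1.4 says that, based on the MRI of a sub-group, "we will further be able to refine validate the HMF technique with the highest accuracy possible". A conjunction seems to be missing, but both verbs rest on the same images. Section 2.3 gives their extent: 12 participants (6 women, 6 men), "who will be scheduled for one visit to the imaging facilities". Sections 2.1, 2.2, 3.1, 3.3 and 4.1 describe MRI only as the reference against which HMF volumes are judged.

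**Changes to HMF in this study.** Section 3.3 plans "adjusting the HMF objective function to incorporate subject-specific thickness of the skin layer based on anthropometric measurements". Section 2.1 adds "the matching of generic model to the study-specific population group including gender". Section 3.1 notes that HMF accuracy depends on the generic model the fit starts from. No section says which data the matched adult model will be built or chosen from. Section 3.3 mentions that the modelling software supplies generic model libraries, which is a possible source.

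**Analysis.** Section 4.1 states: "ANOVA will be performed to analyse the pairwise differences in muscle volumes between the HMF and MRI-based results", at the 0.05 level, following the methods of two earlier studies by the group. It contains no version freeze, no blinding of the modellers to MRI volumes, no split of participants and no cross-validation.

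**The concern.** Error measured in the people used to tune a model is, on average, smaller than its error in new people. Section 1.4, followed as written, would tune and judge HMF on the same 12 people. Table 3.3.2 places the MRI in weeks 0 to 2, so the volumes could be available while HMF is still being changed. A formal refit is not needed for bias: choosing among candidate generic models after seeing which agrees best with MRI has the same effect.

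At stake is the secondary objective. Section 2.1 expects better volume accuracy than the earlier study achieved, and Section 2.3 calls the project confirmatory. If the text stays open, a reader of the results could not tell how much of any improvement came from the new inputs and how much from tuning.

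**Working it through.** **The plan's own figure.** There is none to reproduce. The documents give no sample size calculation, margin or accuracy target for the HMF-MRI comparison.

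**Comparison of the texts**

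| Question | Section 1.4 | Section 3.3 |
|---|---|---|
| Role of the 12 MRI sets | refine and validate | validate |
| Input to the skin-layer change | not stated | anthropometry |
| Source of the matched generic model | not stated | not stated |
| Freeze or out-of-sample step | none | none |

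Reuse of MRI for tuning is therefore permitted and announced in one place, but not confirmed by the operational text.

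**Size if MRI is used (illustration).**
- From the documents: n=12, half of each sex.
- Assumed: a least-squares correction with p free parameters fitted to the 12 HMF-MRI errors; error SD 20% and true bias 20% of volume; covariates beyond sex carry no information.

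Because an offset is included, the ratio of in-sample to new-person error depends on n and p, not on the assumed SD or bias. For p=1 (offset) and p=2 (offset by sex, balanced), with σ the error SD:
- in-sample mean square error = σ²(n−p)/n
- new-person mean square error = σ²(n+p)/n
- ratio of root mean square errors (RMSE) = √[(n−p)/(n+p)]: √(11/13) = 0.920 for p=1 and √(10/14) = 0.845 for p=2

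Simulation with 4,000 runs per row (RMSE in % of volume):

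| p | In-sample | Leave-one-out | New person | In-sample / new | Understated by |
|---|---|---|---|---|---|
| 1 | 19.13 | 20.87 | 20.83 | 0.918 | 8% |
| 2 | 18.26 | 21.91 | 21.56 | 0.847 | 15% |
| 3 | 17.44 | 23.58 | 22.84 | 0.764 | 24% |
| 4 | 16.41 | 25.42 | 24.62 | 0.667 | 33% |

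The first two rows agree with the closed form. Leave-one-out error stays close to the new-person value, at most about 3% above it (25.42/24.62 = 1.03).

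**Effect on the planned test.** With a fitted offset, each residual is the error minus the mean error, so the residuals average exactly zero and a test of the mean difference cannot reject, whatever the true error. A fitted scale factor alone does not do this: least squares then forces the sum of (HMF value × residual) to zero, not the sum of residuals.

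**If MRI is not used.** There is no optimism of this kind, and the test keeps its ordinary power. For a paired t-test at n=12 and two-sided 0.05 (the plan does not state sidedness), power is 0.88, 0.35 and 0.12 for a true bias of 1, 0.5 and 0.25 SD.

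**The case against.** The strongest reply is that dual use of the MRI rests on one imperfect sentence in the background, where one of the two verbs may be a leftover from editing. Every operational section treats MRI as the reference only. The skin-layer change has a stated non-MRI input, and the generic model could come from an existing library. Section 1.2 defines the HMF objective through distances between body-surface points and the model's skin mesh; muscle volume is not a term in it. The methods of the two cited studies cannot be seen here and might include an out-of-sample step. The endpoint is secondary, and Section 3.1 says it is analysed apart from the training intervention.

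Most of this stands, and it limits the point to a conditional one. It does not remove it: the source of the matched model is unstated, accuracy depends on that model, and no text prevents its choice from being guided by the 12 MRI sets.

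A reader might go further in two ways that the documents do not support:
- **That the mean HMF-MRI difference will be zero by construction.** This needs an offset fitted to the same MRI volumes, and no section describes such a fit.
- **That the app's 1RM estimate is tuned on the same participants used to validate it.** Section 1.3 does say that "further development and validation are required to improve the accuracy and reliability in the assessment of exercise execution", and extends this to 1RM. But Section 2.1 attributes the expected gain to added inputs (motion capture and modelled anatomy), and no section describes tuning to the isokinetic values.

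**Conclusion.** The point holds as a conditional one. Sections 1.4 and 3.3 do not agree on the role of the MRI, the source of the matched generic model is missing, and no safeguard separates refinement from validation. If any of the 12 MRI sets inform the generic model or the HMF settings, the reported volume accuracy may be optimistic. The 8% to 33% range shows the possible order of size. It assumes a least-squares correction with 1 to 4 parameters, and the documents give no such number. If MRI is kept out of refinement, the optimism is nil.

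It would be too strong to say that the accuracy is optimistic, or that MRI tuning is the settled plan. The point concerns muscle volume against MRI, not the primary strength endpoint. It should be fixed before the MRI volumes are compared with HMF, because a freeze cannot be added credibly afterwards.

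**What to change.** Reconcile Sections 1.4 and 3.3, and add to Section 4.1:

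1. A statement of whether any of the 12 MRI sets inform the generic model (its construction or its choice) or the HMF objective-function settings, and where the matched generic model comes from.
2. If they do not: freeze and date the generic models and objective-function settings before MRI volumes are opened to the modellers, and report that version as the primary accuracy result.
3. If they do: report leave-one-participant-out error as the accuracy result, with every step that uses MRI, including model choice, repeated without the left-out person. Label in-sample error as development.

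Ultrasound in the 24 participants without MRI (36 − 12) can serve as a supporting out-of-sample check, but only for hamstrings and quadriceps CSA. It cannot validate muscle volume, and it does not cover the triceps surae.

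The cost is wording and some computing. The computing grows if models must be rebuilt for each left-out person, and Section 6.2 itself calls MRI-based modelling very time-consuming. The reported error will probably look less favourable. No additional participants or procedures are needed.
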